### 3.3 Recruitment Process

The study team will develop a SOP on recruitment that is specific to the PWID community. The participants may be recruited using a variety of methods, including referral from harm reduction programs, HIV testing sites, community outreach, and personal referrals. Outreach workers will disseminate information about the study, will provide oral descriptions of the study to prospective participants, and will encourage potential participants to participate in screening activities at the local study site. Potential participants will also be informed that they should pass the information on to other individuals if the study does not apply to them. No scripts or printed materials will be used for recruitment. Recruitment will be conducted at each site separately until the target sample size is reached.

### 3.4 Participant Retention

Once a participant enrolls in this study, the study sites will make every effort to retain him/her for 6 months of follow-up to minimize possible bias associated with loss-to-follow-up. The study team recognizes that PWID represent a heterogeneous population requiring multiple methods to meet their needs, and also recognizes the importance of interacting with the participants in a culturally competent manner. A basic philosophy of the retention strategy is that follow-up begins at recruitment and is a priority at every visit. Components of such procedures include:

- Thorough explanation of the study visit schedule and procedural requirements during the informed consent process, with re-emphasis at each study visit.
- Thorough explanation of the importance of both study arms (intervention and standard of care) to the overall success of the study.
- Collection of detailed locator information at the Screening visit, with active review and updating of this information at each subsequent visit.
- Use of appropriate and timely visit reminder mechanisms.
- Visit calendars, flyers or other handouts will be offered at enrollment to assist with retention.
- Mobilization of trained outreach workers or “tracers” to complete in-person contact with participants at their homes and/or other community locations.
- Regular communication with the study community at large to build trust and increase awareness about substance use treatment and HIV/AIDS.

### 3.5 Participant Withdrawal

Regardless of the participant retention methods just described, participants may voluntarily withdraw from the study for any reason at any time. The Investigator also may withdraw participants from the study in order to protect their safety and/or if they are unwilling or unable to comply with required study procedures after consultation with the Principal Investigator and study clinician. Study staff will record the reason(s) for all withdrawals from the study in participants’ study records.

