#### **2. Informed consent**

Prior to screening, every potential participant demonstrating interest in study participation will have to sign the Informed Consent Form (See Appendix III). Consent procedure will be performed by a study staff member responsible for recruitment. In more details, the consent procedure is described in Section 8.

3. Randomization

Consenting participants will be randomized using the functionality in REDCap participant database using a pre-defined allocation schedule stratified by site.

4. Locator information

After signing the ICF, the participant will provide his contact information. Staff members will assure participants that the detailed follow-up information will be deleted if they are not enrolled in the study.

5. Behavioral and psychosocial survey

Structured interviews will be administered by an experienced interviewer using the questionnaire designed by study team (Appendix II). Baseline and follow-up questionnaires will not differ in content. Interview data will be directly entered into the online version of the participant questionnaire at the REDCap platform.

*Intervention provision (intervention staff)*

6. Assess participant's readiness for PrEP adherence

PNs will use a PrEP readiness tool to assess key predictors of PrEP adherence.

7. PrEP discussion

PrEP Education will be provided at each study visit to participants by PrEP Navigators with the option to start/continue, stop, or abstain from usage. A manual will be created for all sites to follow when discussing PrEP with participants based on safety and efficacy language found in the ICF under "Study Purpose".

8. Autonomy supportive adherence counseling

Adherence counseling will be provided to all participants who initiate PrEP at each study visit starting at the enrollment visit. The counseling makes use of self-determination theory that is designed to facilitate the client's integration of PrEP usage into his health behavioral routines and support the client in making his own decisions regarding adherence. Counseling will include the development of client-centered strategies to support the consistent daily adherence of PrEP. This counseling is delivered one-on-one by PrEP navigators during the study visits. The counseling will also include reminders not to share the medication and to contact project staff with questions about product use.

After each counseling session, the PN will fill out the Care Coordination Measurement Tool (CCMT).

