## **5.7 Premature Study Discontinuation**

Participants may voluntarily withdraw from the study for any reason at any time. Site Coordinators may, with the approval of the PI withdraw participants before their scheduled termination visit to protect their safety, and/or if participants are unable or unwilling to comply with study procedures. Participants also may be withdrawn if the study sponsors, government or regulatory authorities, or site IRBs terminate the study prior to its planned end date. Study staff will record the reason(s) for all withdrawals in participants' study records. The Month 6 visit schedule should be followed when possible, in the event that a participant chooses to withdraw from the study. If a participant chooses to withdraw, data collected from this participant will be deleted and will not be used for analysis. In all other cases, participant information will be used for analysis.

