## 6.2 Adverse Event (AE) Reporting

Adverse events (AE) are defined as any untoward medical occurrence experienced by participants during the study, and may or may not have a causal relationship with the treatment. Information regarding all AEs regardless of seriousness or severity will be recorded in the participant's source files. Grade 3 and higher adverse events and all creatinine AEs will be recorded on study CRFs. All SAEs must be reported on AE Log CRF. All AEs that result in a clinical hold or permanent discontinuation of study product are reported on AE Log CRF regardless of grade. Grade 3 and higher clinical AEs will be referred to a study clinician at the time of the visit.

All critical laboratory values will be reported as applicable per site SOPs. Participants who are not present at the study site at the time a laboratory AE requiring retesting or follow-up is identified will be followed as deemed clinically appropriate. With appropriate permission of the participant, and whenever possible, records from non-study medical providers related to untoward medical occurrences will be requested and required data elements will be recorded on study CRFs and/or in the participant's medical chart. All AEs regardless of severity will be followed clinically, until the AE resolves or stabilizes as per the appropriate toxicity algorithm. AEs will be assessed for all participants, regardless if they continue PrEP or not, after enrollment through the final study visit.

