## 7.0 STATISTICAL CONSIDERATIONS

### 7.1 Review of Study Design

This is an open-label, two-site, two-arm, prospective, randomized controlled trial that aims to assess the initiation, acceptability, safety, and feasibility of daily PrEP for PWID in Ukraine with or without SMS reminder intervention. HIV-uninfected PWID aged 18 and over and at risk for HIV infection will be

recruited and enrolled. Each participant will be offered daily PrEP and followed up to 6 months.

Participants will be followed at the specified study time points and will be evaluated for side effects, adherence, risk behavior and HIV-seroconversion.

**Primary Endpoints:** The primary endpoint of this study is the adherence to PrEP.

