## 7.3 Data Analysis

### 7.3.1 Primary Analyses

#### *PrEP adherence*

For binary outcome of high levels of PrEP adherence (defined as TDF  $\geq$ 700 fmol/punch), generalized estimating equation models (GEE) with binomial distribution will be built to account for correlation in repeated measurements occurring in the same participant. Intervention assignment, time, interaction between time and intervention assignment and any other confounders will be included as covariates. The analysis will be done for repeated measure for both 3 and 6 months. As an alternative analytical plan for assessing the impact of the two intervention arms on adherence to PrEP, continuous version of adherence will be analyzed by using repeated-measures analysis with same set of covariates as the binary outcome and percent change in adherence between different assessment points will be estimated and compared between intervention assignment using linear contrast statement in SAS PROC MIXED. For the above mentioned model, Covariance structure will be selected based on the fit statistics (i.e., AIC, BIC etc.).

There are several strategies by which the PrEP adherence will be measured. We will utilize Spearman correlation coefficients, scatterplots and Kappa statistics to assess associations between the biomedical (TDF concentrations in red blood cells measured via DBS) and self-report measures (VAS: visual analogue scale and 3-item assessment).

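### Staff who know the arm may end a participant's follow-up for non-compliance with study procedures, which adds avoidable and probably informative gaps to the Month 3 and 6 adherence data

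*Protocol*

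**What the plan says.** Two sections allow staff to withdraw a participant from the study. Section 3.5 gives the power to the investigator, after consultation with the Principal Investigator and the study clinician, on grounds of safety or "if they are unwilling or unable to comply with required study procedures". Section 5.7 gives it to site coordinators with the Principal Investigator's approval, again for safety or "if participants are unable or unwilling to comply with study procedures". Neither section defines the procedures meant or sets a threshold. Both require the reason to be recorded.

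Section 5.7 deletes the data of participants who choose to withdraw and uses the data of everyone else. It asks for the Month 6 schedule, where possible, only when the participant chooses to withdraw.

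The surrounding plan is:

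- Section 7.1: "This is an open-label, two-site, two-arm, prospective, randomized controlled trial", and "The primary endpoint of this study is the adherence to PrEP".
- Section 7.3.1, on the GEE for high adherence by DBS: "The analysis will be done for repeated measure for both 3 and 6 months".
- Section 3.4: "the study sites will make every effort to retain him/her for 6 months of follow-up to minimize possible bias associated with loss-to-follow-up". Tracers and outreach are planned for this.
- Section 5.2, item 7: PrEP is discussed at each visit "with the option to start/continue, stop, or abstain from usage".
- Section 6.2: "AEs will be assessed for all participants, regardless if they continue PrEP or not, after enrollment through the final study visit".

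**The concern.** In most trials a clause allowing withdrawal for non-compliance is routine. Here, failing to attend visits or complete assessments lies close to the outcome being measured. The people deciding know the arm, and the decision stops outcome collection as well as treatment.

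The arms may also differ in how often the ground arises. Section 1.1 cites a review in which SMS improved clinic attendance, so missed visits may themselves depend on the arm. SMS customization is done in the experimental arm only (Appendix I), so the two arms do not face quite the same list of procedures.

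At stake are the comparison of arms at Months 3 and 6, the censoring in the persistence analysis, and safety follow-up of participants withdrawn by staff.

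**Working it through.** The protocol gives no expected number of staff withdrawals, so there is no figure of its own to reproduce on this point. Section 7.2 gives only an overall loss to follow-up of 10% to 20%.

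**Step 1. What is lost, by time of withdrawal.**

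| Staff withdrawal | Kept (5.7) | Lost |
|---|---|---|
| Before Month 3 | Enrollment data and any earlier reports | Month 3 and Month 6 DBS, all later self-report |
| After Month 3, before Month 6 | The above plus Month 3 DBS | Month 6 DBS, all later self-report |

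The first group contributes no outcome to the GEE and the second contributes one of two. The exit-visit instruction does not fill the gap. Read literally, Section 5.7 asks for an exit visit from those whose data it then deletes, and not from those whose data it keeps. (The deletion rule is a separate matter.)

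**Step 2. Persistence.** Section 7.1 defines discontinuation as a self-reported run of at least 30 missed days, apart from clinician holds. A gap reported before withdrawal still counts as an event. A gap that begins or completes afterwards is never reported, and the participant is censored. Kaplan-Meier estimation needs censoring to be unrelated to the risk of stopping, which is doubtful when the reason for censoring is disengagement.

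**Step 3. Illustration of size.** Inputs: 100 per arm (200 randomized 1:1, Schema) and true adherence p of 33%, 50% or 67%, the rates in the Section 7.2 table, here applied to a whole arm. Assumptions that the protocol does not supply: w participants are withdrawn in one arm and none in the other; all are non-adherent; all would otherwise have been measured; and missing values are left out of the analysis.

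Observed adherence = 100p / (100 − w).

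| True p | w = 5 | w = 10 |
|---|---|---|
| 33% | 33/95 = 34.7% (+1.7 points) | 33/90 = 36.7% (+3.7) |
| 50% | 50/95 = 52.6% (+2.6) | 50/90 = 55.6% (+5.6) |
| 67% | 67/95 = 70.5% (+3.5) | 67/90 = 74.4% (+7.4) |

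**Step 4. How far this depends on the assumptions, at p = 50% and w = 10.**

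- If the ten have the arm's own mix (5 adherent, 5 not): 45/90 = 50.0%, so no bias.
- If ten are withdrawn in each arm, all non-adherent: 55.6% against 55.6%. The level is inflated but there is no arm difference.
- If missing values are counted as non-adherent: 50/100 = 50.0%, so no inflation.
- If the ten would have given no sample anyway, the clause adds nothing.

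The range is therefore 0 to 5.6 points for this case. The sign of the arm difference depends on which arm loses more. If control participants miss more visits and are withdrawn for it, apparent control adherence rises and a real SMS benefit could be hidden.

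**Step 5. Scale.** The 95% half-width for a difference between two arms of 100 at 50% adherence is 1.96 × √(2 × 0.25/100) = 13.9 points. The illustrative 2.6 to 5.6 points is less than half of that.

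**The case against.** Several points on the other side stand.

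- **Data are kept.** A reader might infer that the clause takes disengaged participants out of the endpoint altogether. Section 5.7 does not support that: their earlier data are analysed, and only later observations go missing.
- **Not taking PrEP is not the ground.** Section 5.2 expressly allows participants to stop or abstain, so non-use of PrEP is not in itself non-compliance. The link to adherence runs through missed visits and assessments and is indirect.
- **There are safeguards.** The Principal Investigator is consulted or must approve, and reasons are recorded. DBS are analysed in batches at the end and individual results are not returned to sites (Section 9.1), so staff cannot select on the biomarker. They see engagement and self-report.
- **The sections do not flatly contradict each other.** Section 3.5 is written knowing that retention efforts come first. Section 6.2 speaks of stopping PrEP, not of leaving the study. The difference over the decision-maker is a mismatch of roles, since the Principal Investigator is involved under both sections.
- **The added loss may be small.** Some of those withdrawn would have missed Months 3 and 6 anyway, and the treatment of missing DBS may be set in an analysis plan that is not at hand.

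None of this removes the point. An analysis rule can assign a value to a missing DBS but cannot recover a sample that the protocol let staff stop seeking. Approval and recorded reasons do not make a decision blind to arm.

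A reader might also want a closed list that limits the end of participation to withdrawn consent, death or study termination. That would delete the safety ground, which is a clinical rule and not a statistical one. It would also collide with Section 5.2, which withdraws participants who test HIV positive at enrollment.

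**Conclusion.** The point holds as an avoidable source of informative missingness. Sections 3.5 and 5.7 let arm-aware staff end outcome collection on a ground that plausibly tracks the outcome, against the aim stated in Section 3.4. It affects the Month 3 and 6 GEE through lost DBS and persistence through informative censoring.

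Neither size nor direction can be derived from the protocol. The shift from 50% to 52.6% or 55.6% illustrates 5 or 10 withdrawals in one arm only, all non-adherent and all otherwise measurable. It is not an estimate, and under other assumptions the effect is zero. The documents do not show that reported adherence will be inflated or that a false arm difference will arise. The case for change is that the loss is avoidable and the change is cheap.

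**What to change.** In Sections 3.5 and 5.7:

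1. Remove non-compliance with procedures, including missed visits or doses, as a ground for ending study participation.
2. State that such participants stay enrolled and are contacted for the remaining visits, with the Month 3 and 6 DBS and survey collected where they agree and can be reached.
3. Extend the exit-visit instruction in Section 5.7 to withdrawals initiated by staff.
4. Report staff withdrawals by arm, with the recorded reasons.
5. Name the same decision-maker in both sections.

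Leave the safety ground in place, but reconcile it with the follow-up through the final visit in Section 6.2, so that it is clear what is still collected from someone withdrawn for safety.

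The cost is a wording amendment to two sections, a line in the reporting, and some extra contact attempts using the tracing already planned in Section 3.4.

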## 4.0 STUDY PRODUCT CONSIDERATIONS

### 4.1 Study Product Formulation/Content/Storage

FTC/TDF is a fixed dose combination tablet containing 200 mg of emtricitabine (FTC) and 300 mg of tenofovir disoproxil fumarate (TDF) in each tablet.

FTC/TDF study tablets must be stored at 25°C, with excursions permitted to 15°C-30°C. FTC/TDF tablets must be stored in the original container. Each container is packaged with a child-resistant screw cap and contains a silica gel to protect the product from humidity.

FTC/TDF 200mg/300 mg is available as Tenof-EM®, a medication registered by the MoH of Ukraine for treatment of HIV-1 infection and for PrEP to reduce the risk of sexually acquired HIV-1 in adults at high risk. Further information on Tenof-EM® is available in the current package insert.

### 4.2 Study Product Regimen, Administration, and Duration

Once enrolled, all participants who agree to initiate FTC/TDF study product will be directed to take one FTC/TDF 200mg/300mg (Tenof-EM®) tablet orally once daily with or without food for up to 52 weeks.

The participant can decide to initiate FTC/TDF administration at any time after enrollment and week 48 of the study treatment period. Once initiated, the study participant may also decide to discontinue taking FTC/TDF study product at any time during the 52 week study treatment period. For participants who decide to initiate PrEP at or after Week 48, partnerships will be established as applicable with community partners in order to provide adequate clinical care and follow-up.

### **4.3 Study Product Supply and Acquisition**

Emtricitabine (FTC) 200 mg/tenofovir disoproxil fumarate (TDF) 300 mg study product tablets are manufactured and provided by Hetero Healthcare, Ltd. FTC/TDF 200mg/300 mg study product will be available through the Kyiv City AIDS Center on general terms.

## **5.0 STUDY PROCEDURES**

An overview of the study visits and procedures schedule is presented in Appendix I and has been written in concordance with current WHO guidelines for PrEP administration. In addition, all providers will be required to follow MOH requirements for the initiation of Tenof-EM for PrEP. Presented below is additional information on visit-specific study procedures. Detailed instructions to guide and standardize all study procedures across sites will be provided in the SOPs.

### **5.1 Pre-screening**

Pre-screening procedures will be conducted by outreach workers and other team members who have access to the target population. The outreach workers will contact potential participants by phone or personally and briefly tell them about the opportunity to participate in a research study.

#### *Pre-screening and screening visit procedures*

#### **1. Briefing**

All potential participants will be informed of the opportunity to participate in the research study. Those who express interest will be informed about the main criteria (emphasizing the HIV-negative status) and rapid HIV testing requirement. If the individual is interested in the study, he will be instructed on where and when the Enrollment visit will take place. A reminder card will be provided. All interested subjects will be referred or accompanied to the clinical study site. Individuals who are not eligible will be informed that they do not meet the requirements of the study and, if necessary, will be referred for appropriate medical services.

### **5.2 Enrollment Visit**

The enrollment visit will take place at a clinical facility designated as a PrEP provider for the study. All procedures will be conducted by the research/intervention staff in close collaboration with the clinical staff. A participant is considered enrolled at the point in time when all enrollment visit procedures are complete.

The following procedures are included in the Enrollment visit (actual sequence may differ).

#### *Administrative and Behavioral Evaluations/ Procedures (research staff)*

#### **1. Eligibility Screening**

Eligibility screening will consist of a brief interview using the Screening Form with the study staff. It will contain basic demographic and HIV risk information.

#### **2. Informed consent**

Prior to screening, every potential participant demonstrating interest in study participation will have to sign the Informed Consent Form (See Appendix III). Consent procedure will be performed by a study staff member responsible for recruitment. In more details, the consent procedure is described in Section 8.

3. Randomization

Consenting participants will be randomized using the functionality in REDCap participant database using a pre-defined allocation schedule stratified by site.

4. Locator information

After signing the ICF, the participant will provide his contact information. Staff members will assure participants that the detailed follow-up information will be deleted if they are not enrolled in the study.

5. Behavioral and psychosocial survey

Structured interviews will be administered by an experienced interviewer using the questionnaire designed by study team (Appendix II). Baseline and follow-up questionnaires will not differ in content. Interview data will be directly entered into the online version of the participant questionnaire at the REDCap platform.

*Intervention provision (intervention staff)*

6. Assess participant's readiness for PrEP adherence

PNs will use a PrEP readiness tool to assess key predictors of PrEP adherence.

7. PrEP discussion

PrEP Education will be provided at each study visit to participants by PrEP Navigators with the option to start/continue, stop, or abstain from usage. A manual will be created for all sites to follow when discussing PrEP with participants based on safety and efficacy language found in the ICF under "Study Purpose".

8. Autonomy supportive adherence counseling

Adherence counseling will be provided to all participants who initiate PrEP at each study visit starting at the enrollment visit. The counseling makes use of self-determination theory that is designed to facilitate the client's integration of PrEP usage into his health behavioral routines and support the client in making his own decisions regarding adherence. Counseling will include the development of client-centered strategies to support the consistent daily adherence of PrEP. This counseling is delivered one-on-one by PrEP navigators during the study visits. The counseling will also include reminders not to share the medication and to contact project staff with questions about product use.

After each counseling session, the PN will fill out the Care Coordination Measurement Tool (CCMT).

9. PrEP Navigation and study product supply

After the brief PrEP discussion, PNs will ensure that each study participant has received the first supply of the medication for one month.

10. SMS reminder customization

The experimental group participants will complete a SMS customization tool, setting key parameters for the intervention (frequency, timing, wording).

11. SMS reminder test

After setting the SMS intervention parameters, a sample message will be delivered to the participant to test the procedure.

12. HIV/ STI behavioral risk-reduction counseling, provision of prevention supplies

Brief risk reduction counseling will be provided to all participants at each visit. These counseling sessions will reinforce the role of consistent use of clean syringes and condoms in HIV/STI prevention, as well as other strategies such as addiction treatment. The overall goal will be to supplement PrEP counseling by supporting participants to adopt or continue risk-reduction practices. Prevention supplies, including clean syringes and condoms will be offered at each visit. Participants will be also provided with information about opioid agonist treatments, and referred to the preferred clinic if necessary.

*Clinical Evaluations/ Procedures (clinical staff)*

13. Medical history including but not limited to co-morbidities, concomitant medications, HIV risk history

The clinician will evaluate medical history of the participant to verify the absence of potential contraindications and drug interactions for PrEP.

14. Symptom-driven physical exam

If any physical or mental symptoms will be expressed by the participant, the clinician will conduct an exam to diagnose the condition and provide appropriate referrals if needed.

Laboratory Evaluations/Procedures (clinical staff)

15. HIV testing

HIV testing will be conducted according to the current HIV testing guidelines by trained staff, with pre- and post-test counseling. According to Ukrainian legislature, HIV diagnosis cannot be made at any setting other than an accredited governmental HIV lab. Therefore, a positive result of rapid testing (regardless of the number of confirmatory runs) will be explained to a subject as preliminary and insufficient to definitively confirm HIV infection, which can be done at specialized health care institutions. As specified in the National HTC guidelines, post-test counseling will provide all details on where the confirmatory testing can be done, and appropriate referrals will be provided.

Participants who test HIV positive will be withdrawn from the study at this point.

16. HBsAg testing

Testing for Hepatitis B is needed because the drugs used in Tenof-EM® can also be used to treat hepatitis B virus and taking Tenof-EM® now might result in less effective treatments for hepatitis B. Testing will be done using a venous blood sample with test kits available at the clinic. Participants positive for HBsAg will be excluded from the study and will be provided appropriate counseling.

17. Blood collection for creatinine test with subsequent calculation of creatinine clearance

To verify eligibility, participants will provide a venous blood sample for the creatinine test. Routinely, the test results will be available within 3 days. Considering the low expected prevalence of elevated creatinine levels, PrEP will be dispensed at the same visit before the creatinine test result is available. If an elevated level is detected, the participant will be contacted, instructed to discontinue PrEP medication and invited for an interim visit to the clinician for a thorough assessment of renal function and possible reasons for elevated creatinine.

18. DBS storage for pharmacology testing

DBS samples will be processed and stored for all participants; testing may be limited to a subset of these samples. DBS will be stored at -20° C within 24 hours of collection and shipped in bulk to a centralized laboratory on dry ice for testing. TDF will be quantified with a validated liquid chromatography tandem mass spectrometry method.

